8 STATISTICS AND DATA ANALYSIS

8.1 Sample size calculation

A minimum of 200 cases is recommended for Structural Equation Modelling (SEM) frameworks⁴⁰. Assuming an attrition rate of 20%⁴¹, recruitment rate of at least 250 subjects should provide this minimum recommended number of cases.

The minimal clinical important difference for the MS-WIS is yet to be established. The MS-WIS has been shown to be predictive of job loss over a 28 month period, following up a cohort of those in work at the onset³⁸.

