8.2 Statistical analysis plan

This is a hybrid trial assessing implementation and effectiveness of the digital READY programme in NHS settings.

In terms of effectiveness, this study seeks to understand who might benefit from the digital READY intervention and in what contexts. Participant outcomes (e.g. Work Instability, Psychological flexibility, Self-efficacy) will be measured at multiple time-points (baseline, week 8 and month 6). While the first step will be to assess for any change to outcome variables over time using repeated measures ANOVA, this provides only an overview of interventional impact and assumes homogenous change within the study group⁴². Latent Growth Curve Modelling (LGCM) can be useful to identify patterns within subgroups of a population to understand who benefits from an intervention and why⁴³. Latent Growth Curve Modelling (LGCM) will be used to determine trajectories over time. Changes from baseline to week 8 and baseline to month 6 will be assessed. Logistic regression models will be utilised to understand potential predictors of these trajectories. Specifically, the relationship between psychological flexibility, resilience, and work instability, how these change for participants from baseline to post-intervention and longer term, and if changes in these variables seem to be linked. If there is evidence of a relationship between work instability and resilience or psychological flexibility over time, such that increases in resilience or psychological flexibility relate to decreases in work instability, this would suggest that the READY programme could be effective in reducing work instability.

Lightning reports will be produced using rapid qualitative synthesis following a pre-defined framework³⁹. These lightning reports will enable iterative assessments of implementation that will inform the final qualitative assessments.

The process evaluation will help to identify contextual factors that may influence core processes of the intervention through qualitative inquiry.

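### Section 8.2 applies logistic regression to growth-curve trajectories that have no categories; it should regress the growth factors on predictors or name a class-based model

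*Protocol*

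**What the plan says.** The effectiveness part of Protocol Section 8.2 opens with its question: "this study seeks to understand who might benefit from the digital READY intervention and in what contexts". Outcomes are taken at baseline, week 8 and month 6. Repeated measures ANOVA comes first and is described as only an overview, because it assumes that everyone changes alike; reference 42 is cited for that remark. The section then gives the reason for the next model, "Latent Growth Curve Modelling (LGCM) can be useful to identify patterns within subgroups of a population", and commits to it: "Latent Growth Curve Modelling (LGCM) will be used to determine trajectories over time". The second stage follows: "Logistic regression models will be utilised to understand potential predictors of these trajectories". A sentence fragment after that turns to psychological flexibility, resilience and work instability, how they change, and "if changes in these variables seem to be linked".

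Section 8.1 sets the sample size on the same modelling framework: "A minimum of 200 cases is recommended for Structural Equation Modelling (SEM) frameworks". With 20% attrition this gives 250 recruits.

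**The concern.** The two stages do not fit together. A conventional LGCM treats the sample as one population and gives each participant a continuous latent intercept and slope. It does not sort participants into groups. Logistic regression needs a grouped outcome, so as written the second stage has no defined dependent variable.

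This is more than detail left to a SAP, because the protocol fixes a pair of methods that do not match. A SAP that follows Section 8.2 inherits the mismatch, and one that departs from it chooses a new model. There are two ways out, and they are different analyses:

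- cut the estimated slopes into groups at a point that the protocol does not give; or
- replace LGCM with a latent class growth or growth mixture model, which does produce groups.

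At stake is the quantitative answer to who benefits. If the choice is made after outcome data are seen, the answer can depend on the cut, and a cut also discards information.

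**Working it through.** **1. The protocol's own figure.** Section 8.1 gives 200 cases and 20% attrition. 200 / (1 − 0.20) = 250, which matches the recruitment target. Section 8.2 gives no alpha, power or effect size for the trajectory step, so everything below rests on stated assumptions.

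**2. What the text supplies and what logistic regression needs.**

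| Needed | In Section 8.2 |
|---|---|
| Growth model that forms groups | LGCM only; no latent class or mixture model named |
| Rule that assigns people to groups | None |
| Cut-off for a grouped outcome | None |
| Binary, ordered or multinomial logistic model | Not said |

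The title of reference 42 concerns latent class growth analysis and growth mixture modelling. This suggests that a class-based model may have been in mind, but the text does not say so.

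**3. Cost of cutting into two groups.** Assume a normally distributed growth factor and small predictor effects. If a share p is placed in one group, the efficiency relative to linear regression on the uncut factor is φ(z_p)² / [p(1 − p)].

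| Split | Efficiency kept | 200 cases act like |
|---|---|---|
| 50/50 | 2/π = 63.7% | 127 |
| 33/67 | 59.5% | 119 |
| 25/75 | 53.9% | 108 |
| 10/90 | 34.2% | 68 |

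The efficiency is highest at the median, so any two-way cut loses at least 100 − 63.7 = 36.3%.

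**4. Cost of ordered groups.** For k equal groups the efficiency is k × Σ(difference of adjacent φ values)². It is 79.3% for k = 3, 86.1% for k = 4 and 89.7% for k = 5, so the losses are 20.7%, 13.9% and 10.3%.

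**5. In terms of power.** A two-sided 5% test with 80% power on the continuous factor has expected z = 1.960 + 0.842 = 2.802. After a median split this becomes 2.802 × √0.637 = 2.235, and power is Φ(2.235 − 1.960) = 61%. A test that starts at 90% falls to 73%. A simulation with 200 cases and predictor correlation 0.197 gave 80.8% (continuous), 61.7% (median split) and 53.0% (25/75 split).

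**6. With slopes estimated from three waves (illustrative).** Assumed, not from the protocol: 200 completers, waves at 0, 8 and 26 weeks, baseline SD 1, residual SD 0.5, true-slope SD 0.5 to 0.7 over 26 weeks, 1,500 runs.

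| Predictor correlation with true slope | Power, continuous slope | Power, median split |
|---|---|---|
| 0.2 | 37% to 52% | 24% to 35% |
| 0.3 | 71% to 86% | 49% to 68% |
| 0.4 | 93% to 98% | 76% to 92% |

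The comparator is linear regression on least-squares slopes, not a conditional LGCM. The table therefore shows the cost of cutting, not the gain from the proposed model.

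**The case against.** The strongest reply is that the authors meant a class-based model. The text objects to homogeneous change, speaks of subgroups and cites a source on class models. Under that reading, multinomial logistic regression on class membership is an ordinary second stage, there is no dichotomisation loss, and the assignment rule could sit in a SAP. This stands as a limit on the size of the problem. It does not rescue the wording, since the model that the protocol commits to is LGCM.

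Four stronger inferences are tempting and are not supported:

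- **The analysis must lose a third or more of the information.** That holds only for a two-way cut. The protocol says neither binary nor where to cut.
- **Treating estimated slopes as known makes the standard errors wrong.** Here the slope is the outcome, so its error goes into the residual. In the step 6 setting, rejection under the null was 4.5% to 5.3%. With slope SD 0.5 and correlation 0.3, the average model standard error against the empirical SD was 0.0596 against 0.0592 (linear) and 0.1475 against 0.1482 (median-split logistic). Power falls, but the standard errors are sound.
- **The protocol assigns the linked-change question to logistic regression.** The fragment follows the logistic sentence but has no main verb, and may equally refer back to the growth model.
- **The sentence on subgroups is itself an error.** LGCM with covariates, or fitted in several groups, can describe growth within known subgroups. What it does not do is find latent ones.

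It is also fair that the first look at change uses ANOVA, which this point leaves untouched, and that contexts are studied in the qualitative process evaluation as well.

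**Conclusion.** The point holds as a mismatch between two named methods. Section 8.2 commits to a model with continuous growth factors and then to a regression that needs categories, and it supplies nothing to connect them. The who-benefits question can be answered within LGCM; the fault lies in the second stage.

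The size is conditional: at least 36% of the information for a two-way cut, about 21% to 10% for three to five equal ordered groups, and no loss of this kind for a class-based model. The first two figures assume a normal growth factor and small effects. The power figures are illustrations under assumed inputs and say nothing about this trial's actual power. The wording should be corrected before outcome data are seen.

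**What to change.** Replace the logistic sentence in Section 8.2, and carry the change into the SAP:

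- **Predictors.** Fit a conditional LGCM in which the latent intercept and slope are regressed on baseline and context predictors, with time scores at 0, 8 and about 26 weeks.
- **Linked change.** Test it as the slope-slope association in a parallel-process LGCM of MS-WIS with psychological flexibility, and in another of MS-WIS with resilience.
- **Subgroups, if wanted.** Name a growth mixture or latent class growth model as exploratory. Relate class membership to predictors by (multinomial) logistic regression with a method that corrects for classification error.

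Any power figures given for this step should be labelled as illustrative and shown over a range of predictor correlations.

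The cost is wording only. The data are those that Section 7.4 already lists, and the models stay within the framework that Section 8.1 uses to justify 200 cases. One dependency needs checking: the change models need MS-WIS at week 8 and month 6. Section 7.4 lists it there, but Table 3, as it reads in the text available, marks it only at screening and baseline. The two should be reconciled.

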1 BACKGROUND

Multiple Sclerosis (MS) is commonly diagnosed between the ages of 20-40¹, a key life stage for working and during which career milestones tend to occur. Despite the majority of PwMS being in work at time of diagnosis, up to 80% have left work within 10-15 years^{2,3}. PwMS are less likely to be in paid employment compared with the general population⁴ and even compared with other chronic conditions⁵. These correlates occur even where there is low physical and cognitive impact⁶ suggesting that psychological barriers and fatigue may be key barriers to job retention^{7,8}.

Low mood and self-efficacy are associated with reduced work participation and declining work performance in PwMS^{7,9,10}. Perceived lack of support and stigmatisation can also lead to negative work outcomes for PwMS^{11,12}. However, over half of PwMS not in paid work report that they "ideally, would like to work"¹³. In addition to financial security, paid employment offers psychological benefits including improved quality of life¹⁴ and self-confidence¹⁵. PwMS who stay in work also report lower symptom incidence¹⁶.

A validated scale for PwMS developed at Leeds can measure and help screen for the risk of job loss (MS Work Instability Scale (MS-WIS)¹⁷). Previous research using this scale has linked risk of job loss to psychological factors such as self-efficacy⁷. An on-going study at Leeds (MS Proactive) has shown that PwMS with lower psychological flexibility tend to have higher work instability (WI; i.e. risk of job loss).

Psychological flexibility, closely linked to resiliency, is the cornerstone of mental health¹⁸ and refers to the ability to effectively manage unwanted inner experiences (e.g., thoughts, memories, bodily sensations) in the present, while adjusting behaviors in the context of changing situational demands to ensure one is behaving consistently with personal values^{19,20}.

A review of psychological interventions for PwMS found a positive impact for both physical and psychological outcomes, including fatigue²¹. One type of psychological intervention called acceptance and commitment therapy (ACT) is an approach underpinned by the psychological flexibility framework. ACT has been shown to significantly improve self-efficacy as well as pain acceptance, low mood and anxiety²².

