3.2 Primary endpoint/outcome

The primary quantitative outcome measures for this study will be work instability, as measured by the MS Work Instability scale, resilience, psychological flexibility, and self-efficacy. We want to check that the digital READY programme will continue to work as

intended when supported by trained healthcare professionals, therefore we would expect to see a psychological benefit for PwMS being supported to use the READY programme in an NHS setting.

We expect that this ACT-based programme should lead to increased resilience, psychological flexibility, and self-efficacy. We theorise that increasing these psychological factors should lead to a reduction in work instability. This should mean we see a significant reduction in work instability in participants who complete the digital READY for MS programme.

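### Section 8.2 leaves self-efficacy out of the linked-change analysis, although section 3.2 makes it a primary outcome and one of three factors expected to lower work instability

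*Protocol*

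**What the plan says.** Section 3.2 lists the primary quantitative outcomes as work instability, "as measured by the MS Work Instability scale, resilience, psychological flexibility, and self-efficacy". It then sets out the theory in two steps. First: "We expect that this ACT-based programme should lead to increased resilience, psychological flexibility, and self-efficacy". Second: "We theorise that increasing these psychological factors should lead to a reduction in work instability". The second step refers back to the first, so three factors are theorised to act on work instability. The trial summary also lists USE-MS among the primary outcomes.

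The Background supports the third factor: "Previous research using this scale has linked risk of job loss to psychological factors such as self-efficacy".

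Section 8.2 opens with all the repeated outcomes in view: "Participant outcomes (e.g. Work Instability, Psychological flexibility, Self-efficacy) will be measured at multiple time-points (baseline, week 8 and month 6". It plans repeated measures ANOVA, latent growth curve modelling, and logistic regression for predictors of the trajectories. It then narrows the question of linked change: "Specifically, the relationship between psychological flexibility, resilience, and work instability". The next sentence says what pattern would suggest that READY could be effective, "such that increases in resilience or psychological flexibility relate to decreases in work instability". Self-efficacy is in neither sentence, and no reason is given.

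USE-MS is scheduled at baseline, week 8 and month 6 (sections 7.3 and 7.4, Table 3).

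**The concern.** Sections 3.2 and 8.2 define the hypothesised mechanism differently. This is not detail left for a later document: 8.2 itself fixes which variables are linked and which pattern counts as support. A SAP that follows 8.2 will not test the self-efficacy link, and one that adds it departs from the protocol.

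Two things are at stake. A theorised pathway, with prior evidence cited in the protocol, would go unreported although the data are collected. And if change in self-efficacy is correlated with change in the other two scales, part of its association with work instability would appear as an association of flexibility or resilience.

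**Working it through.** **1. The two sections side by side.**

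| Place | Self-efficacy | Resilience | Flexibility |
|---|---|---|---|
| 3.2 primary outcomes | yes | yes | yes |
| 3.2 theorised to lower work instability | yes | yes | yes |
| 8.2 outcomes measured over time (examples) | yes | not named | yes |
| 8.2 linked-change sentence | no | yes | yes |
| 8.2 sentence on support for READY | no | yes | yes |

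Nothing elsewhere restores the link. Objective 5 concerns mediation by intervention fidelity, not by self-efficacy.

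**2. The plan's own figure.** Section 8.1 wants 200 cases after 20% attrition: 200 / (1 - 0.20) = 250, as stated. It rests on a rule of thumb for structural equation models, not on the number of factors, so this point does not move it.

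**3. How much could be credited to the wrong scale.** The protocol gives no slopes or correlations, so these are assumptions. Take standardised change scores with a common correlation r among the three factors, and let b be the slope of work-instability change on self-efficacy change. If self-efficacy is left out of a linear regression on the other two, each of their coefficients shifts by b × r / (1 + r). With b = -0.3:
- r = 0.3: -0.3 × 0.3 / 1.3 = -0.07
- r = 0.5: -0.3 × 0.5 / 1.5 = -0.10
- r = 0.7: -0.3 × 0.7 / 1.7 = -0.12

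**4. Worst-case simulation.** Only self-efficacy acts; 200 cases, two-sided 5% tests, 2000 runs per setting. The middle columns give the share of runs with a significant negative link for flexibility or resilience.

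| r (b = -0.3) | Two predictors, joint | Each tested alone | Three predictors | Self-efficacy link found, three predictors |
|---|---|---|---|---|
| 0 | 5% | 5% | 5% | 99% |
| 0.3 | 29% | 39% | 5% | 99% |
| 0.5 | 45% | 73% | 5% | 94% |
| 0.7 | 49% | 93% | 6% | 81% |

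The 5% is chance: two tests, each counted in one direction. For b from -0.2 to -0.4 and r from 0.3 to 0.7, the joint range is 18% to 74%, and the range for separate tests is 23% to 99%.

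**5. The case that section 3.2 describes.** If all three factors act (assumed slope -0.15 each), the two-factor set still finds a flexibility or resilience link in 82% to 97% of runs for r from 0 to 0.7. Little is lost for the general question of whether any link exists. What is lost is the self-efficacy link itself, and the other two coefficients are inflated: at r = 0.5, by -0.15 × 0.5 / 1.5 = -0.05 on -0.15.

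**6. Size of a joint growth model.** A linear parallel-process model over three waves with P processes has 2P means, P(2P + 1) growth-factor variances and covariances, and 3P residual variances.
- P = 3: 6 + 21 + 9 = 36 free parameters; 200 / 36 = 5.6 cases each
- P = 4: 8 + 36 + 12 = 56 free parameters; 200 / 56 = 3.6 cases each

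**The case against.** The strongest reply is that 8.2 contains no regression of MS-WIS change on exactly two change scores. It names ANOVA, growth models and logistic regression, and does not close the list of predictors. The simulation therefore describes a stand-in model. That stands, and the percentages should be read only as an illustration.

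Second, self-efficacy is in 8.2 as a measured outcome. This also stands. A reader might infer that it has been dropped from the analysis altogether, but the text does not support that: its change over time is assessed. Only its link with work-instability change is missing.

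Third, the sentence on support is a hedged sufficient condition about READY as a whole. A reader might infer that the trial would name the wrong active component. The documents do not support this: no objective in 3.1 is to identify one, and where READY works through self-efficacy, a link credited to flexibility still points to the right overall conclusion. A single-arm change-on-change analysis cannot identify an active component by itself, with two predictors or three. Nor does the third predictor fully remove misattribution when scales carry error: with assumed change-score reliability of 0.8 it remains at 8% to 13%, and with 0.6 at 11% to 22% (r from 0.3 to 0.7).

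Fourth, emphasis on flexibility is defensible. The Background places ACT within that framework, and the flow chart's shorter primary list has flexibility but not self-efficacy. But that list also omits resilience, which 8.2 keeps, so it does not explain the choice.

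**Conclusion.** The point holds as an inconsistency between 3.2 and 8.2 with a modest analytical consequence. One of three theorised links is not set down for testing, and whatever it shares with the other two would be credited to them. The joint misattribution of about 29% to 49% is a worst case: it assumes that only self-efficacy acts, a slope of -0.3, r from 0.3 to 0.7 and error-free scales. It is not an expected effect. Under section 3.2's own theory that all three act, the two-factor set would usually still find a link. The mismatch in the text needs none of these assumptions.

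**What to change.** In 8.2, add self-efficacy to the variables in the linked-change sentence, and add an increase in self-efficacy to the patterns listed in the sentence on support for READY. Treat USE-MS in the same way as MPFI and CD-RISC-10: report the link of each with MS-WIS change on its own, and again adjusted for the other two by entering USE-MS change as a third change-score predictor. Do not require a four-process joint growth model, which would raise the free parameters from 36 to 56 at about 200 cases. If the narrower focus is deliberate, say why in 3.2 and 8.2.

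The cost is one more link to examine, and wider intervals for the adjusted flexibility and resilience links when the changes are correlated. With a common correlation r and unchanged residual variance, the standard error grows by the factor (1 + r) / √(1 + 2r): 1.3 / √1.6 = 1.03 at r = 0.3, 1.5 / √2 = 1.06 at r = 0.5, and 1.7 / √2.4 = 1.10 at r = 0.7. No extra data, visits or participants are needed.

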Cardiff

[name]

Email: [contact]

[contact]

[name]

Managing Director and CEO of shift.ms

[name]

Email: [contact]

[contact]

ii. LIST of CONTENTS

GE	NERAL INFORMATION	Page No.
TIT	LE PAGE	1
RE	SEARCH REFERENCE NUMBERS	2
SIG	SNATURE PAGE	3
I. K	EY TRIAL CONTACTS	4
II. L	IST OF CONTENTS	6
III.	LIST OF ABBREVIATIONS	7
IV.	TRIAL SUMMARY	8
V. F	FUNDING AND SUPPORT IN KIND	9
VI.	TRIAL FLOW CHART	12
1	BACKGROUND	13
2	RATIONALE	15
3	OBJECTIVES AND OUTCOME MEASURES/ENDPOINTS	17
4	TRIAL DESIGN	18
5	TRIAL SETTING	21
6	PARTICIPANT ELIGIBILITY CRITERIA	21
7	TRIAL PROCEDURES	22
8	STATISTICS AND DATA ANALYSIS	31
9	DATA MANAGEMENT	32
10	MONITORING, AUDIT & INSPECTION	33
11	ETHICAL AND REGULATORY CONSIDERATIONS	34
12	DISSEMINIATION POLICY	38
13	REFERENCES	39

iii. LIST OF ABBREVIATIONS

Define all unusual or 'technical' terms related to the trial. Add or delete as appropriate to your trial. Maintain alphabetical order for ease of reference.

ACT Acceptance and Commitment Therapy

CI Chief Investigator

GCP Good Clinical Practice

GDPR General Data Protection Regulation

HCP Healthcare Professional ICF Informed Consent Form

IRAS Integrated research application system

ISF Investigator Site File
MS Multiple Sclerosis

MSIS-29 Multiple Sclerosis Impact Scale (29 items)
MS-WIS Multiple Sclerosis Work Instability Scale

MPFI Multidimensional Psychological Flexibility Index
NFI-MS Neurological Fatigue Index for Multiple Sclerosis

NHS National Health Services
PF Psychological Flexibility
PI Principal Investigator

PIS Participant Information Sheet
PPI Patient and Public Involvement
PwMS People with multiple sclerosis
READY(for MS) Resilience for Adults Everyday
REC Research and ethics committee
R&D Research and development

SE Self-efficacy

SUS System useability scale

TMF Trial Master File

TMG Trial Management Group
TSC Trial Steering Committee

USE-MS Uni-dimensional Self-efficacy Scale for Multiple Sclerosis

VAS Visual Analogue Scale

WI Work Instability

iv. TRIAL SUMMARY

Trial Title	Assessing NHS ImplemeNTation of an onlinE Resilience-training Acceptance and Commitment Therapy (ACT) programme to prevent job loss in MS			
Internal ref. no. (or short title)	INTERACT-MS			
Trial Design	Hybrid Feasibility-Implementation Trial			
Trial Participants	(1) MS Healthcare Professionals (2) People with Multiple Sclerosis (in employment)		
Planned Sample Size	(1) 50 (2) 250			
Treatment duration	12 weeks			

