3 OBJECTIVES AND OUTCOME MEASURES/ENDPOINTS

3.1 Aim/s and Objectives

A digital resilience-training programme called 'READY for MS' has been co-developed in the UK and piloted with PwMS who report work instability. It is important to assess that the digital UK READY for MS programme can be delivered and received as intended; this is known as "Intervention fidelity". Specifically, this study aims to monitor fidelity to function, i.e. measuring the core functions of the READY for MS programme, through psychological self-report measures. This is important for checking (validating) the use of READY for MS in a "real world" setting. To do this, we will train MS healthcare professionals to support the delivery of READY for MS and then check whether it has been delivered and received as intended. We will also check that READY leads to the intended long-term outcomes for PwMS who receive it.

Aim: To assess NHS implementation of an online type of Acceptance and Commitment Therapy (ACT) codeveloped with PwMS 'REsilience and Activities for every DaY for MS' (READY) resource to support resilience at work for PwMS.

This will be delivered through five objectives:

- 1. The feasibility and effectiveness of training MS health practitioners in several NHS centres to support delivery of the digital READY programme to PwMS following an immersive training programme.
- 2. The effectiveness of delivering the READY programme in the NHS for PwMS when supported by trained MS practitioners and the long-term outcomes
- 3. Which/how contexts influence how MS practitioners support/engage with PwMS completing the READY programme?
- 4. Which/how contexts influence how PwMS engage with the READY programme and the long-term outcomes
- 5. To what extent intervention fidelity mediates these long-term outcomes

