4 TRIAL DESIGN

This study is a hybrid effectiveness-implementation trial, by which we are simultaneously trialling the effectiveness of an intervention but also exploring its implementation. We will focus on 'fidelity to function', meaning that the intervention still delivers the expected outcomes, while recognising that local adaptation is vital for any intervention to work because every setting and site is different.

We will use purposive sampling for this study, which means we will actively seek to include representatives of different demographic and socio-economic backgrounds.

The trial will include the following phases:

Phase 1: Programme refinement

Findings from the recent co-production and pilot study (MS PROACTIVE) will be utilised to refine and further develop the digital READY programme. The digital programme consists of an introductory module, 6 core modules on ACT factors (Mindfulness, Acceptance, Defusion, Observer Self, Values/Meaningful action, and Future Planning) then a final booster module to be completed after a 5-week break. Aside from the booster module, it is recommended to complete one module per week and each module takes around 40 minutes to complete. There are additional exercises that participants can complete under their own initiative between modules, with accompanying guided audio-recordings (e.g. Mindfulness of the breath). A workbook accompanies the digital content, with reflective written exercises for participants to complete during and between modules. This workbook forms a personal plan that participants can refer back to on completion of the programme.

Phase 2: Getting HCPs READY

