11.3 Public and Patient Involvement

Design: PwMS were involved in the co-development of the MS-Work Instability Scale. This is the primary outcome measure in the MS-PROACTIVE trial.

The 'READY for MS' Acceptance and Commitment Therapy programme was developed by [name] in Australia to improve resilience and self-efficacy. The programme has been tested by PwMS in Australia and in Italy.

The pilot study that precedes this proposal was submitted to the MS Society Research Network for lay review and received positive comments on the importance of research on employment and MS, as well as support for testing of an online intervention.

PwMS were involved in the development and design of the READY digital programme as part of a co-production phase for the current pilot study. Therefore the digital programme that we would now like to trial in an NHS setting has been developed by and for PwMS.

Two occupational therapists provided written feedback at the design stage of this research project. Based on this feedback, we will provide the HCP training sessions in groups virtually to encourage peer support

We submitted this research proposal to the MS society research network and received 4 lay review and 3 peer review responses. PwMS felt positively about a psychological intervention for PwMS who are struggling to stay in work, as well as the potential wider benefits of the READY programme for psychological outcomes. PwMS were also in favour of resources being available online.

Focus groups will be utilised to explore priorities for PwMS and ensure our final study design is in line with these. We will actively recruit people from diverse backgrounds for the focus groups to identify how we might better engage with different communities before recruitment begins.

Management of the research: The Chief Executive of Shift.ms who has multiple sclerosis is an advisor for this project and a member of the Trial Management Group. The Trial Steering Committee will have representation from PwMS.

Participants will be invited to contribute to lightning reports which will inform the ongoing running of the study.

Undertaking the research: 50 HCPs and 250 PwMS will be invited to complete the READY programme. 5 HCPs and 10 PwMS will be invited to complete research interviews which will contribute toward the process evaluation. The embedded process evaluation will be an opportunity to explore qualitatively the contexts that act as barriers or facilitators to people

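### Section 8.2 reads linked change in resilience or flexibility and in work instability as a sign that READY works, which a single-arm cohort cannot support

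*Protocol*

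**What the plan says.** Section 8.2 sets out the effectiveness analysis in steps. It says that "the first step will be to assess for any change to outcome variables over time using repeated measures ANOVA", but describes this as no more than an overview. Latent growth curves and logistic regression follow. The interest is in work instability alongside the two psychological scales: "how these change for participants from baseline to post-intervention and longer term, and if changes in these variables seem to be linked". The section then states how such a link would be read. If gains in resilience or flexibility "relate to decreases in work instability, this would suggest that the READY programme could be effective in reducing work instability".

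There is one treated cohort. Section 11.3 says that "50 HCPs and 250 PwMS will be invited to complete the READY programme". No control group or external comparator is described, and section 2 places a randomised trial after this study.

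Section 3.1 describes the fidelity assessment as "measuring the core functions of the READY for MS programme, through psychological self-report measures", and objective 5 asks "To what extent intervention fidelity mediates these long-term outcomes". Section 3.2 names work instability, resilience, psychological flexibility and self-efficacy as the primary quantitative outcomes.

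**The concern.** Linked change shows that two scales move together within people. It does not show that READY moved either of them. Section 7.4 puts MS-WIS and the psychological scales in the same self-report pack at week 8 and at month 6. A relapse, a low period or a spell of fatigue can shift the answers to both with no help from the programme. Section 1 already reports, without attributing it to READY, that lower flexibility goes with higher work instability.

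The pattern is also separate from average benefit. It can appear when half the sample improves on both scales and half worsens on both, or when the whole group deteriorates. It can be absent when everyone improves by a similar amount.

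Objective 2 concerns effectiveness, and this is the sentence in section 8.2 that says which finding would point to it. Left as written, ordinary covariation between questionnaires could be reported as a sign that READY reduces work instability.

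**Working it through.** **The plan's own figure.** Section 8.1 wants 200 cases after 20% attrition: 200 / (1 - 0.20) = 250. This reproduces the stated target, and n = 200 is used below. The protocol gives no significance level or effect size for this analysis, and no within-person correlation between the scales.

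**Assumptions.**
- A Pearson test of change scores at two-sided 5% stands in for the planned growth-curve and regression models.
- Each standardised score is a stable part (60% of variance) plus a time-varying part (40%).
- The time-varying parts of flexibility and work instability correlate at ρ, varied because the documents give no value.
- The treatment effect is zero on both scales.

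**Correlation of the changes.** The stable parts cancel in the difference. Each change has variance 2 × 0.4 = 0.8 and the covariance is 2 × 0.4 × ρ, so the changes correlate at 0.8ρ / 0.8 = ρ. With 198 degrees of freedom, a correlation of about 0.139 or more in size is significant.

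**Chance of the pattern with no treatment effect.** The Fisher approximation is Φ(atanh|ρ| × √197 - 1.96). For ρ = -0.2 this is Φ(0.2027 × 14.04 - 1.96) = Φ(0.886) = 0.81. A simulation of 4,000 studies per row agrees:

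| Assumed ρ | Significant negative correlation | Mean MS-WIS change significant |
|---|---|---|
| 0 | 2.5% | about 5% |
| -0.1 | 29% | about 5% |
| -0.2 | 81% | about 5% |
| -0.3 | 99% | about 5% |

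These figures are for one pair of scales.

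**Does the pattern track benefit?** Two further simulations:
- Work instability worsens by 0.2 SD and flexibility falls by 0.2 SD, with ρ = -0.3. The pattern still appears in 99% of studies.
- Everyone truly benefits by 0.3 SD on both scales, with ρ = 0. The pattern appears in 3% of studies, while a test of mean change detects the improvement in over 99%.

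**Limit of mean change.** Entry requires MS-WIS of 11 or more, and section 7.1.1 puts 42.8% of an earlier cohort in the low band. Suppose scores are normal, the cut lies at that percentile and the selecting score is also the reference. The expected fall with no effect is then (1 - r) × φ(-0.18) / 0.572 = (1 - r) × 0.686 SD, where r is the test-retest correlation. For assumed r of 0.6 to 0.9 this is 0.27 to 0.07 SD. A fresh baseline measurement after screening would reduce it.

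**The case against.** The strongest reply is that section 8.2 sets no decision rule. The sentence is hedged twice and carries no threshold, significance level or go/no-go. That stands: the protocol overstates what the pattern can show but does not claim proof. Mean change is also already planned as the first step, and section 3.2 expects a significant reduction in work instability. That stands too, although the same section calls the step an overview, and it is equally uncontrolled.

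The percentages rest on assumed correlations and a simplified test. At ρ = 0 the pattern is no more than chance. A reader might infer that it would appear regardless of treatment. The documents support only that it could, wherever the scales co-vary untreated.

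Other stronger readings also go too far:
- A reader might infer that objective 5 is wholly circular. The overlap applies to resilience, flexibility and self-efficacy, which serve both as fidelity measures and as primary outcomes. MS-WIS is a distinct outcome, and section 3.2 states a pathway to it.
- A reader might infer that this correlation will decide on a randomised trial. Section 2 ties preparation for that trial to the process evaluation.
- A reader might infer that delivery goes unrecorded. Notes of the week-3 support contact are scheduled, and the protocol does not say whether the platform logs module use.

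**Conclusion.** The concern holds as an error of stated inference. In a single-arm cohort, linked change in self-report scales is an association consistent with the proposed mechanism. It is not evidence that READY reduces work instability. With no treatment effect, the chance of seeing the pattern runs from 2.5% to 99% as the assumed untreated correlation goes from 0 to -0.3. The documents do not say where in that range the truth lies. The part that does not depend on a particular value is that the pattern neither requires nor tracks a mean improvement in MS-WIS. The planned analysis of mean change does not rescue the inference, since it has no comparator and entry is selected on the outcome scale. Objective 5 has a narrower fault: it uses causal language for an uncontrolled association, and for three of the four primary outcomes its fidelity measure is also the outcome.

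**What to change.** 1. Replace the sentence in section 8.2 so that a link between change in resilience or flexibility and change in work instability is reported only as an association consistent with the proposed mechanism, and not as evidence that READY reduces work instability.
2. Rest any statement on work instability on the mean MS-WIS change from baseline to month 6, which the planned first step already examines. Give it a 95% CI and describe it as uncontrolled and open to regression to the mean because of the entry threshold. Use the baseline MS-WIS as the reference, not the screening score.
3. In objective 5, write 'is associated with' in place of 'mediates', and limit the analysis to month-6 MS-WIS adjusted for baseline.

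Section 7.4 lists MS-WIS at month 6. In the copy read here, Table 3 marks it only at screening and baseline, so check that the two agree.

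The cost is wording in the protocol, and in the SAP if there is one. Design, sample size and questionnaires are unchanged. The downside is a more modest claim.
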